#### **4.5.3 Treatment Discontinuation Criteria**

Nivolumab treatment should be permanently discontinued for the following:

- Any Grade 2 drug-related uveitis, eye pain, or blurred vision that does not respond to topical therapy and does not improve to Grade 1 severity within the re-treatment period OR requires systemic treatment
- Any Grade 3 non-skin, drug-related AE lasting  $> 7$  days, with the following exceptions for laboratory abnormalities, drug-related uveitis, pneumonitis, bronchospasm, neurologic toxicity, hypersensitivity reactions, infusion reactions, and endocrinopathies:
  - Grade 3 drug-related uveitis, pneumonitis, bronchospasm, neurologic toxicity, myocarditis, hypersensitivity reaction, or infusion reaction of any duration requires discontinuation
  - Grade 3 drug-related endocrinopathies adequately controlled with only physiologic hormone replacement do not require discontinuation. Adrenal insufficiency requires discontinuation regardless of control with hormone replacement.
  - Grade 3 drug-related laboratory abnormalities do not require treatment discontinuation except:
    - Grade 3 drug-related thrombocytopenia  $> 7$  days or associated with bleeding requires discontinuation
    - Grade  $\geq 3$  drug-related AST, ALT or total bilirubin requires discontinuation\*
    - Concurrent AST or ALT  $> 3 \times$  ULN and total bilirubin  $> 2 \times$  ULN
- \* In most cases of Grade 3 AST or ALT elevation, study drug(s) will be permanently discontinued. If the investigator determines a possible favorable benefit/risk ratio that

warrants continuation of study drug(s), a discussion between the investigator and the BMS Medical Monitor/designee must occur.

- Any Grade 4 drug-related adverse event or laboratory abnormality (including but not limited to creatinine, AST, ALT, or total bilirubin), except for the following events which do not require discontinuation:
  - Grade 4 neutropenia  $\leq$  7 days
  - Grade 4 lymphopenia or leukopenia or asymptomatic amylase or lipase
  - Isolated Grade 4 electrolyte imbalances/abnormalities that are not associated with clinical sequelae and are corrected with supplementation/appropriate management within 72 hours of their onset
    - Grade 4 drug-related endocrinopathy adverse events, such hyper- or hypothyroidism, or glucose intolerance, which resolve or are adequately controlled with physiologic hormone replacement (corticosteroids, thyroid hormones) or glucose-controlling agents, respectively, may not require discontinuation after discussion with and approval from the BMS Medical Monitor.
- Any event that leads to delay in dosing lasting  $>$  6 weeks from the previous dose requires discontinuation, with the following exceptions:
  - Dosing delays to allow for prolonged steroid tapers to manage drug-related adverse events are allowed. Prior to re-initiating treatment in a subject with a dosing delay lasting  $>$  6 weeks from the previous dose, the BMS medical monitor must be consulted. Tumor assessments should continue as per protocol even if dosing is delayed. Periodic study visits to assess safety and laboratory studies should also continue every 6 weeks or more frequently if clinically indicated during such dosing delays.
  - Dosing delays lasting  $>$  6 weeks from the previous dose that occur for non-drug-related reasons may be allowed if approved by the BMS medical monitor. Prior to re-initiating treatment in a subject with a dosing delay lasting  $>$  6 weeks, the BMS medical monitor must be consulted. Tumor assessments should continue as per protocol even if dosing is delayed. Periodic study visits to assess safety and laboratory studies should also continue every 6 weeks or more frequently if clinically indicated during such dosing delays.
- Any adverse event, laboratory abnormality, or intercurrent illness which, in the judgment of the investigator, presents a substantial clinical risk to the subject with continued nivolumab dosing.

#### **4.5.4 Nivolumab Treatment Beyond Disease Progression**

Accumulating evidence indicates a minority of subjects treated with immunotherapy may derive clinical benefit despite initial evidence of PD. Subjects treated with nivolumab will be permitted to continue nivolumab treatment beyond initial RECIST 1.1 defined PD until the maximum of 24 months from the first treatment, assessed by the investigator, as long as they meet the following criteria:

- Investigator-assessed clinical benefit
- Tolerance of study drug

[figure not shown]
- Stable performance status
- Treatment beyond progression will not delay an imminent intervention to prevent serious complications of disease progression (eg, CNS metastases)
- Subject provides written informed consent prior to receiving additional nivolumab treatment. All other elements of the main consent including description of reasonably foreseeable risks or discomforts, or other alternative treatment options will still apply.

A radiographic assessment/ scan should be performed within 6 weeks of initial investigator-assessed progression to determine whether there has been a decrease in the tumor size or continued PD. The assessment of clinical benefit should be balanced by clinical judgment as to whether the subject is clinically deteriorating and unlikely to receive any benefit from continued treatment with nivolumab.

If the investigator believes the subject would receive clinical benefit by continuing nivolumab treatment after scans showing disease progression, the subject may continue to receive nivolumab treatment, remain on the trial, and monitored according to the Time and Events Schedule in [Section 5](#).

When a subject receives nivolumab therapy beyond disease progression, further progression from initial progressive disease evaluation is defined as an additional 10% increase in tumor burden (with a minimum 5 mm absolute increase). This includes an increase in the sum of diameters of all target lesions and/or the diameters of new measurable lesions compared to the initial progressive disease evaluation. Nivolumab treatment should be discontinued permanently upon determination of further progression.

New lesions are considered measurable at the time of initial progression if the longest diameter is at least 10 mm (except for pathological lymph nodes which must have a short axis of at least 15 mm). Any new lesion considered non-measurable at the time of initial progression may become measurable and therefore included in the tumor burden if the longest diameter increases to at least 10 mm (except for pathological lymph nodes which must have a short axis of at least 15 mm). In situations where the relative increase in total tumor burden by 10% is solely due to inclusion of new lesions which become measurable, these new lesions must demonstrate an absolute increase of at least 5 mm.

#### **4.5.6 Treatment of Nivolumab-Related Infusion Reactions**

Since nivolumab contains only human immunoglobulin protein sequences, it is unlikely to be immunogenic and induce infusion or hypersensitivity reactions. However, if such a reaction were to occur, it might manifest with fever, chills, rigors, headache, rash, pruritus, arthalgias, hypotension, hypertension, bronchospasm, or other allergic-like reactions. All Grade 3 or 4 infusion reactions should be reported within 24 hours to the study medical monitor and reported as an SAE if it meets the criteria. Infusion reactions should be graded according to NCI CTCAE (Version 4) guidelines.

Treatment recommendations are provided below and may be modified based on local treatment standards and guidelines, as appropriate:

For Grade 1 symptoms: (mild reaction; infusion interruption not indicated; intervention not indicated):

- Remain at bedside and monitor subject until recovery from symptoms. The following prophylactic premedications are recommended for future infusions: diphenhydramine 50 mg (or equivalent) and/or acetaminophen/paracetamol 325 to 1000 mg at least 30 minutes before additional nivolumab administrations.

For Grade 2 symptoms: (moderate reaction required therapy or infusion interruption but responds promptly to symptomatic treatment (eg, antihistamines, non-steroidal anti-inflammatory drugs, narcotics, corticosteroids, bronchodilators, IV fluids); prophylactic medications indicated for  $\leq$  24 hours):

- Stop the nivolumab infusion, begin an IV infusion of normal saline, and treat the subject with diphenhydramine 50 mg IV (or equivalent) and/or acetaminophen/paracetamol 325 to 1000 mg; remain at bedside and monitor subject until resolution of symptoms. Corticosteroid and/or bronchodilator therapy may also be administered as appropriate. If the infusion is interrupted, then restart the infusion at 50% of the original infusion rate when symptoms resolve; if no further complications ensue after 30 minutes, the rate may be increased to 100% of the original infusion rate. Monitor subject closely. If symptoms recur, then no further BMS-936558 will be administered at that visit.
- For future infusions, the following prophylactic premedications are recommended: diphenhydramine 50 mg (or equivalent) and/or acetaminophen/paracetamol 325 to 1000 mg should be administered at least 30 minutes before nivolumab infusions. If necessary, corticosteroids (up to 25 mg of hydrocortisone or equivalent) may be used.

For Grade 3 or 4 symptoms: (severe reaction, Grade 3: prolonged [ie, not rapidly responsive to symptomatic medication and/or brief interruption of infusion]; recurrence of symptoms following initial improvement; hospitalization indicated for other clinical sequelae (eg, renal impairment, pulmonary infiltrates). Grade 4: Life threatening; pressor or ventilatory support indicated):

- Immediately discontinue infusion of nivolumab. Begin an IV infusion of normal saline and treat the subject as follows: Recommend bronchodilators, epinephrine 0.2 to 1 mg of a 1:1000 solution for subcutaneous administration or 0.1 to 0.25 mg of a 1:10,000 solution injected slowly for IV administration, and/or diphenhydramine 50 mg IV with methylprednisolone 100 mg IV (or equivalent), as needed. Subject should be monitored until the Investigator is comfortable that the symptoms will not recur. Nivolumab will be permanently discontinued. Investigators should follow their institutional guidelines for the treatment of anaphylaxis. Remain at bedside and monitor subject until recovery of the symptoms.

In case of late-occurring hypersensitivity symptoms (eg, appearance of a localized or generalized pruritus within 1 week after treatment), symptomatic treatment may be given (eg, oral antihistamine or corticosteroids).

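### Protocol Section 4.5.6 is internally inconsistent on symptoms that recur after an interrupted Grade 2 infusion is restarted: the Grade 2 block reads as allowing later dosing, while the Grade 3 definition covers recurrence and requires permanent discontinuation

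*Protocol*

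**What the plan says.** Protocol Sections 4 and 4.5 send sites to Section 4.5.6 for acute infusion reactions. That section asks for grading by NCI CTCAE version 4 and gives management steps by grade.

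- **Grade 2, restart.** "If the infusion is interrupted, then restart the infusion at 50% of the original infusion rate when symptoms resolve".
- **Grade 2, recurrence.** "If symptoms recur, then no further BMS-936558 will be administered at that visit".
- **Grade 2, later visits.** The next bullet begins "For future infusions, the following prophylactic premedications are recommended". It does not separate subjects whose symptoms recurred from those whose symptoms did not.
- **Grade 3, definition.** The parenthesis opens by calling the reaction severe. Its listed elements include "recurrence of symptoms following initial improvement; hospitalization indicated for other clinical sequelae".
- **Grade 3 or 4, action.** "Nivolumab will be permanently discontinued".
- **Reporting.** Grade 3 and 4 infusion reactions go to the medical monitor within 24 hours. Section 4.5.6 sets no such rule for Grade 2.

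Section 4.5.3 states the stopping rule separately: "Grade 3 drug-related uveitis, pneumonitis, bronchospasm, neurologic toxicity, myocarditis, hypersensitivity reaction, or infusion reaction of any duration requires discontinuation". Section 3.5 makes the Section 4.5.3 criteria mandatory. The introduction to the management steps in Section 4.5.6 calls them recommendations that may be adapted to local standards. Section 4.5.3 has no such clause.

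**The concern.** A site that restarts a Grade 2 infusion and sees the symptoms return will be reading the Grade 2 block. That block limits the stop to the current visit and moves on to preparing for later ones. A few lines below, the Grade 3 definition describes the same sequence of events and leads to a permanent stop. No sentence tells the site to regrade the reaction, or says that it stays Grade 2.

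Subject safety is at stake first: whether a subject with a failed restart receives nivolumab again depends on which text the site applies. The 24-hour report is also triggered under only one of the two. The trial has no data monitoring committee (Protocol Section 7; SAP Section 2.5) that might otherwise notice uneven handling.

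There is a smaller effect on the safety results. AEs leading to discontinuation are a named safety measure (Protocol Section 8.3.2.5) and are tabulated by worst grade within tumor group (SAP Section 7.6.3). The general AE tables are also by worst grade (SAP Section 7.6.5). SAP Section 7.2.2 counts study drug not given per protocol as a relevant deviation, so a site that followed the Grade 2 block could be recorded as having deviated from Section 4.5.3.

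**Working it through.** The plan gives no figure on this point, so no arithmetic applies. The check follows one case through the text.

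1. A subject has a Grade 2 reaction and the infusion is stopped.
2. Symptoms resolve and the infusion restarts at half rate. Resolution is the stated condition for restarting, so any symptoms that return after a restart done as instructed come after an improvement.
3. Symptoms return. The texts then compare as follows.

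| Question | Grade 2 block, Section 4.5.6 | Grade 3 text, Section 4.5.6, with Section 4.5.3 |
|---|---|---|
| Does it cover recurrence? | Yes, as a management step; no grade is assigned to the recurrence | Yes, as an element of the definition |
| Drug at this visit | Stopped | Stopped |
| Drug at later visits | Not stated outright; the stop is limited to the visit and the next bullet covers future infusions without exception | Permanent discontinuation |
| 24-hour report to the medical monitor | Not required for Grade 2 | Required |
| Force of the text | Recommendation, locally modifiable | Section 4.5.3 is a requirement, mandatory through Section 3.5 |

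The two columns agree on the immediate action and differ on later dosing and reporting.

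4. Does another passage resolve the difference? The CTCAE instruction names one grading standard, but Section 4.5.6 does not say that a recurrence triggers regrading. Section 4.5.3 settles what happens once an event is called Grade 3; it does not say whether this event is Grade 3. Its closing criterion, which stops treatment when the investigator sees substantial clinical risk, leaves the matter to judgment. None of these removes the inconsistency.

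**The case against.** The case against has four parts.

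- **One grading standard.** A reader might infer that the protocol gives the same event two grades. It does not. All infusion reactions are graded by CTCAE, and the Grade 2 definition, as distinct from its management step, does not mention recurrence. What stands is that the step sits under the Grade 2 heading with no prompt to regrade.
- **No express permission to re-dose.** A reader might infer that the two instructions are opposite and that the protocol authorizes re-exposure after recurrence. No sentence says so. Stopping for the visit is compatible with stopping for good, and the future-infusions bullet also serves subjects without recurrence. Later dosing is inferred from two adjacent bullets. That inference is natural because the bullet carries no exception, but it remains an inference.
- **Unequal force.** The steps in Section 4.5.6 may be modified locally, while Section 4.5.3 is binding. A site that has called the event Grade 3 therefore has a clear rule. This does not help the site that is still deciding the grade.
- **Severity.** The Grade 3 parenthesis opens by describing a severe reaction, so a mild recurrence could be held to stay Grade 2. That is a fair reading. Recurrence is nevertheless listed as its own element with no further threshold, so two careful investigators could disagree.

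On the tables, grade should follow CTCAE and not the paragraph a site happened to use. Misgrading is possible but is not built into the plan. The discontinuation tables are more exposed, because they record what was done.

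**Conclusion.** The inconsistency is real and should be corrected because it bears on whether a subject is dosed again. It is an internal contradiction in the text, not a design choice. It is confined to later dosing and 24-hour reporting after a failed restart, with a possible knock-on effect on the worst-grade and AE-leading-to-discontinuation summaries. The ORR analysis, power and sample size do not depend on it.

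Its frequency cannot be derived from the documents, which give no infusion-reaction rate. Purely as an illustration, assume that 1% to 5% of the maximum 350 subjects have an interrupted and restarted infusion, and that 20% to 33% of those recur. The result runs from 350 × 0.01 × 0.20 = 0.7 to 350 × 0.05 × 0.33 = 5.8 subjects. Both rates are assumptions, so this shows only that the number is probably small.

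A reader might also infer that one such subject must shift a group's rate by at least 4 percentage points (1/25). The documents do not support that as a floor: Protocol Section 8.1 lets the sponsor allow a group more than 25 subjects. The same arithmetic would hold for any single adverse event. The point rests on the conflicting text, not on a count.

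**What to change.** Reconcile three places: the Grade 2 block of Section 4.5.6, the Grade 3 definition in the same section, and the infusion-reaction criterion in Section 4.5.3. State once how symptoms that recur after a restart are graded, including whether severity matters. Then make dosing at later visits and the 24-hour report follow from that grade, and word the Grade 2 future-infusions bullet so that it is clear whether it applies to subjects with recurrence. The sponsor makes the clinical choice; this review takes no view on which rule is right.

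The cost is about one sentence in Section 4.5.6, made in the next amendment or by administrative letter. No new procedures, data collection or changes to the statistical analysis are needed.

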#### **4.6 Blinding/Unblinding**

Not applicable.

#### **4.7 Treatment Compliance**

Treatment compliance will be monitored by drug accountability as well as the subject's medical record and eCRF.

#### **4.8 Destruction or Return of Investigational Product**

For this study, IP (those supplied by BMS, a vendor or sourced by the investigator) such as partially used study drug containers, vials and syringes may be destroyed on site (see below).

If	Then
IP supplied by BMS (including its vendors)	Any unused IP supplied by BMS can only be destroyed after being inspected and reconciled by the responsible Study Monitor unless IP containers must be immediately destroyed as required for safety, or to meet local regulations (eg, cytotoxics or biologics).

It is the investigator's or designee's responsibility to arrange for disposal, provided that procedures for proper disposal have been established according to applicable federal, state, local, and institutional guidelines and procedures, and provided that appropriate records of disposal are kept. The following minimal standards must be met:

- On-site disposal practices must not expose humans to risks from the drug.
- On-site disposal practices and procedures are in agreement with applicable laws and regulations, including any special requirements for controlled or hazardous substances.

- Written procedures for on-site disposal are available and followed. The procedures must be filed with the site's SOPs and a copy provided to BMS upon request.
- Records are maintained that allow for traceability of each container, including the date disposed of, quantity disposed, and identification of the person disposing the containers. The method of disposal, ie, incinerator, licensed sanitary landfill, or licensed waste disposal vendor must be documented.
- Accountability and disposal records are complete, up-to-date, and available for the Monitor to review throughout the clinical trial period.

It is the investigator's or designee's responsibility to arrange for disposal of all empty containers.

If conditions for destruction cannot be met the responsible Study Monitor will make arrangements for return of IP provided by BMS (or its vendors). Destruction of non-IP sourced by the site, not supplied by BMS, is solely the responsibility of the investigator or designee.

Please refer to [Section 9.2.2](#) for additional guidance on IP records and documentation.

#### **4.9        Retained Samples for Bioavailability / Bioequivalence**

Not applicable

## 5 STUDY ASSESSMENTS AND PROCEDURES

### 5.1 Flow Chart/Time and Events Schedule

**Table 5.1-1: Screening Procedural Outline CA209627**

Procedure	Screening Visit	Notes
Eligibility Assessments		
Informed Consent	X	
Inclusion/Exclusion Criteria	X	All inclusion/exclusion criteria should be assessed at screening and confirmed prior to first dose
Medical History	X	Including diagnostic pathology report
Prior Systemic Therapy	X	
Safety Assessments		
Physical Examination	X	Within 14 days prior to first dose
Physical Measurements	X	Include Height and Weight Within 14 days prior to first dose
Vital Signs	X	Temperature, BP, HR, and RR within 3 days of first dose
Performance Status (ECOG)	X	Within 14 days prior to first dose. See Appendix 2 for ECOG scale
Assessment of Signs and Symptoms	X	After obtaining Informed Consent, assess all signs and symptoms within 14 days prior to first dose.
Concomitant Medication Collection	X	Within 14 days prior to first dose
Serious Adverse Events assessment		Assessed using NCI CTCAE v. 4 (continuously evaluate after subject signs ICF)
Laboratory Tests	X	Screening local laboratory assessments should be done within 14 days prior to first dose and are to include: CBC with differential, Chemistry panel including LFTs (ALT, AST, total bilirubin, alkaline phosphatase), albumin, BUN or serum urea level, creatinine, Ca, Na, K, Cl, phosphate, LDH, glucose, and thyroid panel including TSH, free T3, and free T4.  The following screening local laboratory assessments should be done prior to first dose: Hepatitis B and C testing (HBV sAg and HCV Ab or HCV RNA).
HIV testing (Germany only)	X	

**Table 5.1-1: Screening Procedural Outline CA209627**

Procedure	Screening Visit	Notes
Pregnancy Test	X	Serum or urine pregnancy testing at screening visit and repeated within 24 hours of first dose. [REDACTED]
[REDACTED]	[REDACTED]	[REDACTED] [REDACTED]
[REDACTED]	[REDACTED]	[REDACTED] [REDACTED]
IVRS/Clinical Drug Supplies		
Phone calls to IVRS	X	Phone calls must be made to IVRS as follows: 

• For subject number assignment at the time informed consent is obtained.

• Prior to dosing for study drug vial assignment (call should be made within 3 days prior to dosing).

**Table 5.1-2: On-Treatment Assessments - Nivolumab 240mg/Q2 weeks CA209627**

Procedure	Cycle 1 Day 1 (C1D1) (First dose)	Each Cycle (every 2 weeks) on Day 1	Notes:
Safety Assessments			
Physical Examination (including weight)	X		
Targeted Physical Examination		X	Targeted examination must include at a minimum the following body systems: Cardiovascular, Gastrointestinal, and Pulmonary. Weight must be collected. Within 3 days prior to dosing
Vital Signs	X	X	Temperature, BP, RR, and HR. Obtain vital signs within 3 days prior to dosing.
ECOG Performance Status	X	X	See Appendix 2 for ECOG scale
Adverse Events Assessment	----- Continuously -----		Assessed using NCI CTCAE v. 4
Serious Adverse Event Assessments	----- Continuously -----		Assessed using NCI CTCAE v. 4.
Review of Concomitant Medications	X	X	
Laboratory Tests	X	X	On-study local laboratory assessments should be done within 3 days prior to dosing for every cycle and to include: CBC with differential, Chemistry panel including LFTs (ALT, AST, total bilirubin, alkaline phosphatase), BUN or serum urea level, creatinine, Ca, Na, K, Cl, phosphate, LDH, and glucose. If > 14 days from screening, labs must be repeated.
Thyroid Function Testing		See Notes	TSH (reflex to free T3 and free T4 if abnormal result) to be performed every 6 weeks ( $\pm$ 1 week).
Pregnancy Test	X	See Notes	Serum or urine within 24 hours prior to first dose and then at least once every 4 weeks regardless of dosing schedule.

